Treatment devices: TAP 1 (Airway Management Inc., Dallas, TX; MT type OA device) and SomnoDent Flex (SomnoMed, Plano, TX; BT type OA). Both OA devices will be used per manufacturers' recommendations. To insure comparability, both devices have a custom thermal acrylic liner insuring a very accurate fit. Each subject will also be custom fitted with a mandibular positioner ("AM Aligner" or "Morning Positioner") to use for up to 20 minutes after awakening in the morning; this will assist in returning the subject to his/her normal occlusion.

Appliance Acclimation: Both appliances will be adjusted / titrated to the patient's maximal comfortable protrusive position by patient in the wake state. The starting position will be determined by the patient at a comfortable position but not less than 60% as determined by the Pro Gauge. "Comfortable" is defined as the advanced mandibular position that permits the subject to sleep for ≥ 5 hours per night for at least 6 nights of the week. Subjects will use diaries to record appliance settings and hours of sleep on each sleep recorded or non-recorded night. Two follow-up nights (post T_1) of SleepImage recordings only will be made to track sleep quality and OA position, if further mandibular adjustments are necessary as determined by the T_1 & T_3 HST and SleepImage results.

Course of Treatment: Subjects will be randomly assigned to either the MT- or BT-first OA device as treatment for OSA. Each subject will use the first OA for 4 weeks followed by – 1 week washout period that includes using nightly their prescribed CPAP and daytime use of a mandibular positioner (for up to 20 minutes) – then another 4 weeks of active treatment with the second OA.

h. Power Analysis and Sample Size

At least 38 subjects with OSA are needed to yield a power of 0.90 with alpha = .05 and an expected Effect Size of at least a 10 point difference in the post-treatment mean RDI scores between MT vs. BT devices.Recruitment will be extended to n=44 to accommodate an estimated 20% drop-out rate. The projected numbers are based on Wilcoxon signed-rank test where the expected difference between-treatments (cross-over design) is expected to be at least 10 point difference in RDI scores.

i. Statistical analyses

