Wilcoxon signed-rank test (matched pairs) for cross-over design for primary variables will be used. For dichotomous secondary variables, data analysis will use logistic regression to adjust for effects of initial severity, age, gender, BMI, ethnicity, SES, phenotypic differences, etc. t-tests and Mann-Whitney tests as needed for non-dichotomous outcomes, depending upon normality. Descriptive statistics (means, standard deviation, medians, interquartile ranges) for each outcome measure will be calculated and bar, boxplot or line graphed for each time point. Repeated measures analysis of variance, parametric or nonparametric one-way analysis of variance, as appropriate, will be used to determine if each of the outcome measures vary across the time points.

1. Handling of missing data

For the primary study endpoint, several methods will be used, including: 1) last observation carried forward, 2) multiple imputations, and 3) imputing a missing value with the group's mean value at that follow-up and frequency.

The set of missing data analyses will serve as a sensitivity analysis for the primary study outcomes. If the data imputation methods for a given endpoint result in disparate statistical inferences, the differences will be investigated and elucidated in the final clinical study report.

j. Right and Safety of Research Participants

The clinical trial will be conducted in accordance with the ethical principles that have their origin in the Declaration of Helsinki and the Belmont Report and that are consistent with Good Clinical Practice (GCP). The laws, regulations and rules of the United States, the state of Texas and the Texas A&M University pertaining to human subjects research will be followed. The rights, safety, and well-being of the trial subjects are the most important considerations and will prevail over the interests of science and society. The available clinical information on the OA devices is adequate to support the proposed clinical trial.

Freely given informed consent will be obtained from every subject prior to clinical trial participation. All patient clinical trial information will be recorded, handled and stored in a way that allows its accurate reporting interpretation and verification. The confidentiality of records that could identify subjects will be protected, respecting the privacy, confidentiality rules and to ensure non-bias reporting requirements.

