b. After meeting the study's inclusion and exclusion criteria through telephone screening, study subjects will receive detailed information about the study from the Study Coordinator during their first appointment. The first appointment to the study center will include obtaining a copy of the patient's PSG/CPAP study reports and medical history, completion of the study's intake assessment, signing the informed consent form and obtaining impressions and protrusive bite. In the absence of a current PSG, subjects will be sent home with a HST to collect comparable baseline information. Both oral appliances will be constructed prior to the second appointment. The subjects will be randomized to an OA device at second appointment (this will allow any questions by the lab of the dentist to improve the device). During the second appointment, subjects will be examined and fitted by the dentist with both OAs. Subjects will be then scheduled within 4-weeks for the first HST with simultaneous SI recording for determination of the RDI and sleep quality criteria. Recordings will occur x1/subject at T₁ (first night in week-1 with first OA), T₂ (after four weeks using first OA), a washout period of 1 week using a mandible repositioner daily and CPAP nightly, T₃ (first night of week-6 with second OA) and T₄ (after four weeks using second OA). (Figure 1, below; Table 1)

c. Table 5: Protocol for determining subject candidacy:

EVALUATION	PURPOSE	PROCEDURE/RATIONALE
Recruitment / Orientation	Provide information about the study.	Provide the subject with information regarding the OA devices, the clinical study and an information brochure.
Medical Background Information	Gather information regarding the subject's medical background to determine candidacy, and recent sleep study evaluations.	Standard medical case history and physical with emphasis on OSA to include the Medical/Surgical History as part of the Case Report. Conducted individually by the team/Study Coordinator and discussed collectively to ensure that the subject has realistic expectations for the study.
Craniofacial & Oral Testing	Verify subject qualification with a craniofacial / oral exam.	Clinical assessment is performed to examine the upper airway and oropharynx to determine the subject qualification for using OA therapy.
Informed Consent	Obtain informed consent.	Informed consent will be obtained by providing information related to the time commitments of the trial, risks and contraindications.

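### Single group-mean imputation, and LOCF not confined to one device, are not sound sensitivity checks for the paired primary RDI comparison

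*Combined protocol and SAP*

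**What the plan says.** All references are to the combined protocol and SAP.

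- **Primary test (VII.i):** "Wilcoxon signed-rank test (matched pairs) for cross-over design for primary variables will be used". The treatment of zero differences is not stated.
- **Missing data (VII.i.1):** "For the primary study endpoint, several methods will be used, including: 1) last observation carried forward, 2) multiple imputations", and thirdly replacing a missing value by the group's "mean value at that follow-up and frequency". Group is not defined, LOCF is not limited to values from the same device, and no imputation model is given.
- **Role (VII.i.1):** "The set of missing data analyses will serve as a sensitivity analysis for the primary study outcomes". If the methods "result in disparate statistical inferences", the plan requires the differences to be looked into and explained in the final report.
- **Timing (abstract; IX.b):** T1 and T2 are the first and last recordings on the first device, T3 and T4 on the second. T3 is the "first night of week-6 with second OA". Table 4 in VII.e labels T2 and T3 the other way round; the two must be reconciled before any carry-forward rule can be read.
- **Adjustment (VII.g):** extra recordings are foreseen "if further mandibular adjustments are necessary as determined by the" T1 and T3 results, so a first-night value can precede a change of setting.
- **Expected loss:** 44 are recruited "to accommodate an estimated 20% drop-out rate" (VII.h); 13.1 gives 10-20% and says about 38 must complete. Under 16.1 a subject may leave at any time if an appliance proves unsuitable.

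**The concern.** A sensitivity analysis should show whether the primary conclusion survives a different, defensible treatment of the missing values. Two of the three named methods may not do so in a paired crossover.

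Filling with a device or sequence mean treats an invented value as an observation. The test then counts more pairs than exist, so a significant complete-pair result is confirmed too easily.

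LOCF raises a different problem. A subject lost after T2 and before T3 has only first-device values. If T2 is carried to T4, the first device's RDI stands in for the second device's and the paired difference is exactly zero. With zeros dropped, the test cannot disagree with the complete-pair test. The plan's follow-up rule is triggered only by disagreement, so agreement that the method itself forces passes unnoticed.

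**Working it through.** **Inputs from the plan.** 44 enrolled, 38 completers, a 10-point RDI difference, power 0.90, alpha 0.05, 10-20% dropout. Losses examined: 6 (44 - 38) and 9 (0.20 x 44 = 8.8).

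**The plan's own figure.** No SD is given, so 38 cannot be reproduced. Solving the two-sided signed-rank approximation for the SD of paired differences gives 10 x sqrt(38 x 3/pi) / (1.96 + 1.28) = about 18.6. The runs below used 18.4 or 18.6.

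**Assumptions not in the documents.** That SD; between-device correlation r of 0.3, 0.5 or 0.7; random loss; 22 subjects per sequence.

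**1. Device-mean fill, 9 of 44 lacking T4.** Let D be the SD of differences and s^2 = D^2 / [2(1 - r)] the variance of one RDI value. A real difference has variance D^2; a filled one has about s^2.

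- Reported SE = sqrt{[(35/44)D^2 + (9/44)s^2] / 44}
- Actual SE = sqrt{s^2 [2/39.5 - 2r x 35/39.5^2]}, with on average 39.5 observed values per device
- Complete pairs: 18.4/sqrt(35) = 3.11

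| r | Reported SE | Actual SE (formula) | Actual SE (simulated) |
|---|---|---|---|
| 0.3 | 2.69 | 3.00 | 2.97 |
| 0.5 | 2.77 | 3.09 | 3.09 |
| 0.7 | 2.96 | 3.29 | 3.28 |

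The reported SE is about 10% too small in each case. At r = 0.5 the effective critical value is 1.96 x 2.77/3.09 = 1.76, a two-sided error of about 0.079. This is a large-sample check on the mean. Simulation of the signed-rank test itself gave:

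| Loss pattern | Device- or sequence-mean fill | Complete pairs |
|---|---|---|
| 6 of 44 lack T4 | about 0.06-0.07 | about 0.05 |
| 9 of 44 lack T4 | about 0.07-0.08 (runs from 0.067 to 0.084) | about 0.05 |
| 9 lost, about half lacking both T2 and T4 | about 0.10-0.11 | about 0.05 |

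At a true 10 points, r = 0.5 and 9 missing, apparent power rises from 0.86 to 0.90-0.91. At r = 0.3 part of such a gain is real (actual SE 2.97 against 3.11), but the reported SE is still too small.

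**2. Fill with the mean of all subjects at the visit.** The filled value is midway between devices, so a filled pair carries on average 5 of the 10 points. Expected difference: 10 x (38 + 3)/44 = 9.3 with 6 filled, and 10 x (35 + 4.5)/44 = 9.0 with 9. Simulated type I error stays between 0.044 and 0.055.

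**3. LOCF from T2 to T4.** Each filled difference is 0. Expected mean difference: 10 x 38/44 = 8.6 with 6 filled, and 10 x 35/44 = 8.0 with 9. With zeros dropped, the signed-rank result is identical to complete pairs (type I error 0.048, power 0.86 at r = 0.5). With zeros kept in the ranking (Pratt), power is about 2 points lower with 9 filled.

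**4. LOCF from T3 to T4, same device.** With about half of the losses after T3 and loss random across sequences, type I error was 0.047-0.052, even with first-night RDI set 5 or 10 points worse.

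**5. Multiple imputation.** With first-period RDI, baseline and sequence in the model, 20 imputations, and the signed-rank Z pooled by Rubin's rules, type I error was 0.040-0.052. The mean difference was 9.9-10.1 at a true 10.

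**The case against.** The plan has a safeguard: discordant results must be investigated and explained, and no rule lets the most favourable method decide. The list is open-ended and already contains multiple imputation. The inflation depends on how an undefined word is read, and its size on an assumed SD, correlation and loss pattern. Recordings are tied to devices, so LOCF may be meant within device; a subject lost before T3 would then have nothing to carry forward. Losses may also be fewer than assumed, since 13.6 allows a faulty recording to be repeated.

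Much of this stands and keeps the point small. It does not remove it. Defining group does not rescue the method, because one reading understates the standard error and the other shrinks the estimate. The safeguard acts on disagreement only.

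Three stronger readings are tempting and not supported:

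- **That the primary result is compromised.** The methods are labelled sensitivity analyses. A matched-pairs test and a requirement for 38 completers imply complete pairs, although the plan does not say so outright.
- **That LOCF favours a positive finding.** Across devices it pulls towards no difference.
- **That within-device LOCF is biased.** No bias in the test was shown. Cancellation between sequences needs losses to be balanced, but nothing in the documents indicates that they would fall in one sequence. What remains is a caveat: a first-night value is set against a week-4 value.

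**Conclusion.** The point holds as a low-priority improvement to the sensitivity analyses. Under either reading of group, single mean imputation is not a sound check. By device or sequence it raises two-sided type I error to about 0.06-0.07 (6 missing) or 0.07-0.08 (9 missing), and to about 0.10-0.11 if about half of the 9 lack both values. By visit across all subjects it shrinks 10 points to about 9. The direction under device or sequence means was the same in every scenario run; the sizes rest on the assumed SD, correlation and loss pattern.

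The LOCF fault is conditional on values crossing devices, which the text permits but does not prescribe. In that case LOCF is conservative and close to a restatement of the complete-pair test.

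**What to change.** In VII.i.1:

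1. Delete single group-mean imputation.
2. Bar carrying a value from one device to the other. If LOCF is kept, limit it to the same device and label it as using a first-night value.
3. Make the planned multiple imputation the main sensitivity analysis. Name the model (the other period's RDI, baseline AHI, sequence) and the rule for pooling the signed-rank statistic, for example Z pooled by Rubin's rules.
4. State in VII.i that the primary signed-rank test uses complete T2/T4 pairs.

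Optionally, add one delta-adjusted imputation: 16.1 links withdrawal to an unsuitable appliance, and standard multiple imputation assumes data missing at random.

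The cost is SAP wording and modest programming. The downside is a shorter list of sensitivity analyses. Design and sample size are unchanged.

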Sleep breathing disorders which includes obstructive sleep apnea (OSA) snoring, has an estimated prevalence of 3 - 7% of the adult US population. OSA subjects experiencing chronic sleep debt and intermittent nocturnal hypoxia are more prone to health risks that includes carbohydrate metabolism imbalance, immune and endocrine dysfunction (Table 1).² Continuous positive airway pressure (CPAP) is the American Academy of Sleep Medicine (AASM) treatment recommendation for this highly prevalent disorder. However, approximately 30% of OSA patients do not tolerate CPAP.4

Alternative treatment options for OSA include surgical interventions, mandibular advancement splint also referred to as oral appliance (OA) therapy, tongue retaining and hypoglossal nerve stimulating devices, but these have debatable efficacy in moderate and severe OSA. Efficacy differences in OA therapies treatment of moderate and severe OSA could be related to OA design variations although this hypothesis has not been tested. Hoekema et al. (2007b) used a custom-fitted midline traction (MT) OA and found large improvements in Epworth Sleepiness Scale (ESS) scores, oxygen saturation levels, Quality of Life, Short Form (SF)-36 scores and the apnea hypopnea index (AHI) in a randomized control trial (RCT) in severe OSA subjects. ⁵ Three other RCT studies from

Hoekema (2007a, 2008a, 2008b) and two other reports also used the same MT-device in moderate and severe OSA patients. ⁶⁻¹⁰ AHI improvements ranged from 80 to 90% (mean 85%). In contrast, several studies in moderate and severe OSA patients using bilateral thrust (BT) design failed to demonstrate an AHI reduction <10 events/hour although showing >50% AHI reduction (mean 55.4%; range 53 – 57%) from baseline conditions. ¹³⁻¹⁹ Of the OA studies considered in the American Academy of Dental Sleep Medicine (AADSM) practice guidelines, four (67%) used a MT OA, compared with only one (14%) in seven studies that used BT OA in severe OSA subjects (Table 2).²⁰ The mean pre-OA AHI was 40.1 events/hour that reduced to a mean 5.7 events/hour post-treatment in the MT OA reports. The single BT OA study in severe subjects had a pre-treatment AHI equal to 30 events/hour that reduced to 14 events/hour at post-OA treatment.

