b. Population

- 1. Adults (n=44) with moderate to severe OSA.
- 2. Potential study participants will be recruited by means of flyers posted at the College of Dentistry, Dallas A.W.A.K.E. office (support group for sleep apnea patients) and Dallas area sleep clinics. Online postings at clinicaltrials.gov and the College web site. Also post flyers at (1) regional hospitals and clinics, (2) city and county offices/stations (such as the Dallas Fire Department), (3) DART and other transportation offices and (4) Facebook, Twitter and similar site, (5) local newspapers and magazines, (6) local radio stations. The content of the advertisements on venues (5) and (6) will be the same as the approved flyers. Written permission will be sought from all sites at which flyers are to be posted. Data analyst and subjects will be blinded to treatment device type (i. e. sequence of use of the two OAs) and subject's identity will be coded.
- 3. Controls and Controlling Confounders: Subjects serve as their own controls; their baseline polysomnography (PSG) or Home Sleep Test (HST), untreated values (from full or split night PSGs) will serve as their control values for evaluating treatment effects with each of the two OAs. The focus of the trial is on comparing OA appliance efficacy in reducing the RDI (AHI); the presentation, fitting, monitoring and adjustment of the two OAs will be the same for both arms of the study. For the operators, there will be concealed allocation of assignment of subjects to treatment.
- 4. Performance Site: Texas A&M College of Dentistry, [name]. Seventh floor room 725, two operatory clinic.

c. Inclusion criteria

OSA diagnosed adults, at least 18 years old, who have been recently diagnosed by polysomnography (PSG) or polygraphy home sleep test (HST) in the previous year and are currently being treated with continuous positive airway pressure (CPAP) having an AHI > 15 events/hour of sleep; two or more OSA symptoms (snoring, witnessed apnea or daytime hypersomnolence complaint); at least 8 teeth per arch to support either OA device; Mallampati score from I to III; Palatine tonsils – grade 0, 1, or 2; Central and mixed apnea index < 5 events /hour. Consent to study's timeline; willingness to wear home sleep test apparatus for at least 4 nights and to wear an oral appliance every night for 8 weeks; willingness to pick up and return home sleep test kits as needed.

d. Exclusion criteria

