We do not anticipate any significant physical risk from participating in this study. Though unlikely, some subjects may experience itching or rashes from the adhesive hypoallergenic electrodes of the Medibyte or the SleepImage devices. The pulse oximeter may cause some minor irritation of the finger or finger nail. By wearing an OA, a subject may experience some discomfort and/or reduced function of the jaw joint (temporomandibular joint) and muscles of the jaw (masticatory muscles) and of the face during and after treatment. Subjects may also experience some reduction in sleep quality due to discomfort while getting used to wearing the OA (acclimation). Other minor risks include temporary irritation of the mouth and oral cavity due to contact with the OA, and excessive salivation or dry mouth from mouth breathing. Repositioning of the lower jaw and tooth movement may also occur, but are typically minor and reversible. Also highly unlikely, a subject could swallow or aspirate part of an OA should it break.

I. Potential benefits to subjects

- Two customized oral appliances to keep upon completion of the study at no cost to the subject (value of \$4600)
- 2. Effective devices that do not require electricity to operate, so can be used anywhere
- 3. Reduced apnea and snoring
- 4. Improved sleep quality and continuity

- 5. An effective treatment for obstructive sleep apnea that does not require wearing a face mask
- 6. No air pressure blowing through nose
- 7. Receiving information on sleep quality.
- 8. The researchers or study coordinator will discuss possible options that might be of benefit if a sleep issue is discovered.

Study Limitations

Hyperarousal response to the OA. Possible brief OA acclimation (4-weeks) and washout (1-week) period. No placebo device as a control condition. Interrater variability of HST polygraphy scoring. No controlled sleep environment which allows for variability in external conditions during sleep recordings. Absence of conventional sleep staging based on EEG activity.

- Adverse events and adverse device effects
 - 1. Definitions
 - i. Adverse Event (AE)

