Each participants involvement in the study while at home is as follows: On each of 4 nights over the course of 9 weeks the subject will put on the HST and SI prior to bedtime, and remove them upon awakening. The two systems include attaching sensors to various parts of the face, chest and abdomen. Adhesive pads and surgical tape are used to hold these devices and wires in place. Placement may take up to 20 minutes, and removal, about 5 minutes. The coordinator will demonstrate how to apply the sensor properly to insure valid recordings. Minor discomfort may be experienced when pulling off the tape. If a first night recording is faulty, a subject may be asked to do a second night recording: subjects will not be asked to record for more than 8 nights in total. Subjects will wear an OA every night for 4 weeks, no OA for the 1-week washout period, and an OA (the alternate device) for each night for another 4 weeks. They will put on the OAs prior to bed and remove them upon awakening. The OA will contain a computer chip that will also record the actual amount of time that the OA is worn each night. Subjects use their CPAP devices each night of the washout period as prescribed by their physicians. Some discomfort and/or tendeness in the temportomandibular joint (jaw joint or TMJ) and jaw muscles may be experienced during and after OA use. Also some minor tooth movement and discomfort may be experienced. In addition to their OAs, each subject will be given a mandibular repostioner, a small custom bite splint to be worn for two minutes after removing the OA upon awakening. Use of the mandibular repostioner will minimize or eliminate the aforementioned discomforts and tooth movement. All of this clinical care, potential discomforts and tooth movements will be carefully monitored and managed by the dentists on the research team.

How long will the participants be engaged in the research (length of time, e.g., 15 minutes, 45 minutes on Day 1, 60 minutes on Day 2, etc.)?

Visit 1: 120 minutes; Visit 2: 60 minutes; Visits 3-9: 15 minutes each. Total in office commitment: Approximately 5 hours. For the home sleep tests, approximately 30 minutes for at least 4 nights(but no more than 8 nights), for a total of at least 2 hours (but no more than 4 hours)

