By wearing an OA, a subject may experience some discomfort and/or reduced function of the jaw joint (temporomandibular joint) and muscles of the jaw (masticatory muscles) and of the face during and after treatment. Subjects may also experience some reduction in sleep quality due to discomfort while getting used to wearing the OA (acclimation). Other minor risks include temporary irritation of the mouth and oral cavity due to contact with the OA, and excessive salivation or dry mouth from mouth breathing. Repositioning of the lower jaw and tooth movement may also occur, but are typically minor and reversible. Also highly unlikely, a subject could swallow part of an OA should it break.

Describe the approaches you will take to minimize these risks and/or to minimize their impact.

Participants will be carefully monitored for all of these risks (above) by one or more of the study dentists. The subjects will be able to contact a member of the research team 24/7 to address any concerns.

What alternatives are available to subjects outside the research (i.e., what is the standard of care, is the research intervention available without participating)?

No alternative treatment options are available as part of this study. If a prospective subject decides that either oral appliance therapy is not suitable, the alternative is to not enroll in the study and continue CPAP therapy as prescribed. Once enrolled in the study, if the subject decides that either oral appliance therapy is not suitable at any time, he/she may withdraw from the study and continue with CPAP therapy as prescribed.

16.2 What are the potential benefits of this study to individual participants? (This does not include payments, compensation, or incentives.)

The benefits of taking part in this study are:

- 1. Two customized oral appliances are yours to keep upon completion of the study at no cost to you
- 2. Effective devices that do not require electricity to operate, so can be used anywhere
- 3. Reduced apnea and snoring
- 4. Improved sleep quality and continuity
- 5. An effective treatment for obstructive sleep apnea that does not require wearing a face mask
- 6. No air pressure blowing through your nose
- 7. Receiving information on your sleep quality.

The researchers or study coordinator will discuss with you possible options that might be of benefit to you if a sleep issue is discovered.

16.3 What are the potential benefits of this study to the population or society?

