- How will the device be used? Each of the test custom-fitted OAs will be worn each night during sleep for a 4-week period with a 1-week washout period between test OAs. The subject is expected to wear their prescribed CPAP during the washout period. The HST recorders to evaluate sleep quality with OA use will be obtained by study subjects for each of the two OA testing periods on the first and last day of each 4-week period. A total of 4 sleep recordings/subject is expected over the 9-week study period.
- How will the device be destroyed and disposed? The HST recorders are reusable/non-disposable items, so they will not be destroyed.
- Alternatives available to patients: No alternative treatment options are directly part of this study.
 If a prospective subject decides that either oral appliance therapy is not suitable for him/her, the
 alternative is to continue to use his/her prescribed CPAP therapy.

26.0

Before you Submit

26.1 Please note the following.

The following checklist is a guide for researchers regarding supporting documents that must be considered for and/or uploaded with this application for review and approval before use.

- Informed Consent Document
- Information Sheet
- Waiver of HIPAA Authorization
- Parental Permission Form/Minor Assent Form
- Recruitment materials (i.e. flyers, emails, advertisements, telephone scripts, social media posts)
- Site Authorization Letter (for study conduct and/or access to administrative records)
- Survey/Questionnaire/Data Collection/Abstraction Forms
- Grant Applications (cover to cover), required if funded or grant submitted
- Instructions
- Protocol Investigator's Brochure (for clinical trials only)
- Case report form (for clinical trials only)
- Device Manual (if using an approved or investigational device)
- Thesis/dissertation proposal
- Waiver of parental permission/minor assent form
- Letter of cultural evaluation for international research (link to SOP)
- IRB approvals from collaborating institutions
- Any other documents related to the research
- CVs for all investigators when proposed activities are more than minimal risk
- CITI training for all personnel

Investigators assume the following responsibilities:

- Continuing Review: The study must be renewed by the expiration date in order to continue with
 the research. A Continuing Review application along with required documents must be submitted
 by the continuing review deadline. Failure to do so may result in processing delays, study

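### Residual sleep apnea is missing from the listed and monitored risks, and there is no written step for a poor responder whose appliance adjustment fails

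*Combined protocol and SAP*

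**What the plan says.** All places are in the combined protocol and SAP. The trial is a crossover of a midline traction (MT) and a bilateral thrust (BT) appliance.

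- **Population (VII.c).** Adults who "are currently being treated with continuous positive airway pressure (CPAP) having an AHI > 15 events/hour of sleep". There is no upper AHI limit and no CPAP-adherence requirement.
- **CPAP during the trial.** VII.g describes a "1 week washout period that includes using nightly their prescribed CPAP". Section 13.6 says "Subjects use their CPAP devices each night of the washout period as prescribed by their physicians", and 25.2 says "The subject is expected to wear their prescribed CPAP during the washout period". No text assigns CPAP during the two appliance periods. That it stops then is implied, not stated.
- **Risks (VII.k, 16.1).** VII.k says "We do not anticipate any significant physical risk from participating in this study". The two sections list sensor irritation, jaw-joint and muscle effects, tooth movement, mouth irritation, saliva changes, appliance breakage, and poorer sleep from discomfort during acclimation. Neither names residual or under-treated sleep apnea.
- **Monitoring (16.1).** "Participants will be carefully monitored for all of these risks (above) by one or more of the study dentists".
- **Use of the early recordings (VII.g, Appliance Acclimation).** Follow-up SleepImage nights are made "if further mandibular adjustments are necessary as determined by the" T1 and T3 home sleep test (HST) and SleepImage results. VII.l adds that options will be discussed if a sleep issue is found.
- **Expected effect (I. Abstract).** "The single BT OA study in severe subjects had a pre-treatment AHI equal to 30 events/hour that reduced to 14 events/hour at post-OA treatment".

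**The concern.** Replacing CPAP is the largest change the trial makes to a subject's care, and incomplete control of the apnea is its most foreseeable consequence. The protocol's own background says that appliances have debatable efficacy in moderate and severe disease and that untreated disease carries health risks. Yet this consequence is outside the risk lists, and so outside the monitoring commitment that refers back to them.

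The T1 and T3 recordings could detect it, but their only written consequence is mandibular adjustment. There is no threshold and no next step. If adjustment fails, the subject stays on the appliance until T2 or T4 unless he or she withdraws or a clinician steps in without a stated criterion. The next scheduled HST is at the end of that 4-week period.

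**Working it through.** **1. Exposure.** From VII.g: 4 × 7 = 28 nights per appliance, so 56 of 9 × 7 = 63 nights have no assigned CPAP.

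**2. The plan's own BT figure.** The printed improvements in the seven BT rows of Table 2 are 56, 56, 56, 53, 55, 57 and 55%. Their mean is 388/7 = 55.4%, range 53 to 57%, which reproduces the figure in the Abstract.

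**3. Group means against the protocol's own marks.**

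| Mark | Source | Seven BT means (11.1 to 14/h) | Six MT means (3.2 to 8.4/h) |
|---|---|---|---|
| below 10/h | II, therapeutic goal | all miss, by 1.1 to 4.0/h | all meet |
| more than 50% reduction | II.c and V, alternative arm of the acceptable level | all meet (53 to 57%) | all meet (64 to 90%) |
| 15/h | VII.c, entry threshold | all below, by 1.0 to 3.9/h | all below |

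The average BT subject in these studies therefore reaches the acceptable level through the percentage arm.

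**4. What the means leave open.** BT baseline means run from 25.6 to 30/h. Entry has no upper limit, so BT results above 30/h cannot be read from Table 2. No individual spread is given, so the number of poor responders cannot be calculated.

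**5. How possible safety criteria would behave.** A plain limit of 10/h would fail all seven BT group means, and T1/T3 are untitrated first nights, so it would flag too many subjects. Now take RDI at or above 15/h **and** less than 50% below baseline B, that is, RDI ≥ 15 and RDI > B/2. No BT row meets either part. For assumed individual baselines:

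- B = 20/h: flagged from 15/h (a reduction of 25% or less).
- B = 30/h: flagged above 15/h.
- B = 40/h: flagged above 20/h.

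This picks out poor responders rather than the typical BT subject. Its weak side is very severe disease: at an assumed B = 60/h, a fall to 30/h is not flagged.

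**6. Which recording can confirm it.** VII.f derives RDI from the polygraph, which has airflow and oximetry. SleepImage is described with ECG, actigraphy, position, snore and ECG-derived respiration, and it gives no RDI. The follow-up SleepImage nights therefore cannot show that an RDI criterion has been resolved; a repeat HST is needed.

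**7. Room for it.** Section 13.6 caps recording at 8 nights. Four scheduled HST nights leave 4. If SleepImage-only nights count toward the cap, 8 − 4 − 2 = 2 remain, or 8 − 4 − 4 = 0 if such nights follow both T1 and T3.

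**The case against.** The case for leaving the plan alone is substantial. Residual disease is what the trial measures, at four time points. The protocol describes appliances as first-line for mild to moderate and second-line for severe disease. VII.d excludes cardiac and pulmonary disease and BMI of 35 or more. Section 16.1 gives 24/7 contact and withdrawal to CPAP at any time, VIII makes a qualified dentist responsible for care, and 13.6 provides Visits 3 to 9. Adverse events are defined to include those unrelated to the device. Diaries and the Epworth scale are also collected.

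These points reduce the risk and rule out calling the trial unprotected. None of them puts residual apnea among the monitored risks or supplies a criterion. Epworth scores come at baseline, T2 and T4, so they give no early warning within a period.

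Two objections to the remedy also stand and shape the fix:

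- **Loss of pairs.** Returning subjects to CPAP removes pairs from the matched Wilcoxon analysis. If these are mainly the worst BT responders, the remaining pairs favour BT.
- **Expectedness.** The adverse-event section defines an unexpected event as one not mentioned in the protocol, and suspension depends partly on unexpectedness. Listing the risk without qualification could weaken that trigger.

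**Conclusion.** The gap is real and should be closed, but it is narrow. It concerns individual subjects whose apnea stays poorly controlled after adjustment, for up to 28 nights per appliance. Their number is unknown. The conclusion assumes that CPAP stops during the appliance periods, as the design implies.

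A reader might infer more than the documents support:

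- **That 56 nights of effective treatment are lost.** CPAP adherence at entry is not required. The Abstract puts CPAP intolerance at about 30%, and II.b says appliance compliance is greater. The net loss is unknown.
- **That BT leaves the typical subject inadequately treated.** All seven BT means meet the percentage arm and lie below 15/h.
- **That subjects are not told.** The consent pages were not available, so this cannot be judged.

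VII.k and 16.1 also differ on the bite-splint comparison and on aspiration. Those are minor wording points and not part of this finding.

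**What to change.** 1. **Risk lists.** Add residual or under-treated sleep apnea during the appliance periods to VII.k and 16.1, which brings it under the 16.1 monitoring. State that a serious or unexpectedly severe event from it is still handled under the reporting and suspension rules. Change the consent form only if it has the same gap.

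2. **Safety review of T1 and T3.** Have the responsible clinician review these results, already read for titration, against a criterion fixed before enrolment. One example is RDI at or above 15/h and less than 50% below baseline; the investigators may add an absolute ceiling for very severe disease. Titrate first, confirm on a repeat HST within the 8-night cap, and return the subject to CPAP if the finding persists. State whether SleepImage-only nights count toward the cap.

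3. **Analysis.** Record each return by device and period. VII.i.1 allows last observation carried forward; do not carry the untitrated first-night T1 or T3 RDI forward as T2 or T4. Use the post-titration HST value, or a single-night T2/T4 recording on the appliance if the clinician judges it safe. Report a sensitivity analysis that treats returns as non-response to that device.

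**Cost.** Wording in two sections, one review step on existing recordings, and a few repeat HST nights with device issue and return. Some early returns will be outcome-related, possibly more on BT. Those that leave no usable value draw on a margin of 44 − 38 = 6 losses from all causes.
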